7.6.2.1 Lack of Efficacy or Worsening of Rheumatoid Arthritis

Medical occurrences or symptoms of deterioration that are anticipated as part of RA should be recorded as an AE if judged by the Investigator to have unexpectedly worsened in severity or frequency or changed in nature at any time during the study. When recording an unanticipated worsening of RA on the AEs eCRF page, it is important to convey the concept that the condition has changed by including applicable descriptors (e.g., “accelerated RA”). Events that are clearly consistent with the expected pattern of progression of the underlying disease, as determined by the Investigator, should not be recorded as AEs; these data will be captured as efficacy assessment data only. Every effort should be made to document progression using objective criteria. If there is any uncertainty as to whether an event is an AE or due to disease progression, it should be reported as an AE.

Any worsening of RA that meets the criteria for seriousness should be reported as an SAE.

7.6.2.2 Overdose

Study treatment overdose is the accidental or intentional use of the drug in an amount higher than the dose being studied. An overdose or incorrect administration of study treatment is not an AE unless it results in untoward medical effects. Any study treatment overdose or incorrect administration of study treatment should be noted on the Study Drug Administration eCRF. All AEs associated with an overdose or incorrect administration of study treatment should be recorded on the AEs eCRF page.

7.6.2.3 Reporting and Follow-Up Requirements for Pregnancies

Pregnancies in Female Subjects

A serum pregnancy test will be conducted on all females of childbearing potential at Screening, and urine pregnancy tests will be conducted thereafter as presented in the Schedule of Events (Table 1 or Table 2 [as applicable]).

If a subject becomes pregnant after the administration of any study treatment, R-Pharm and/or R-Pharm’s designee should be informed immediately. Study treatment should be discontinued as soon as the pregnancy is known and the following should be completed:

- The subject should immediately discontinue further administration of study treatment.
- The subject should return for an EoT Visit.

- All scheduled safety assessments must be performed unless contraindicated by pregnancy (harmful to fetus) or the subject withdraws informed consent.

The Investigator must inform the subject of information currently known about potential risks and about available treatment alternatives. The pregnancy should be followed-up to determine outcome, including spontaneous or voluntary termination, details of the birth, and the presence or absence of any birth defects, congenital abnormalities, or maternal and/or newborn complications.

Full details will be recorded on a Pregnancy Report eCRF and submitted via the Electronic Data Capture (EDC) system, and reporting details will be detailed in the study manual. The Investigator will update the Pregnancy Report eCRF with additional information as soon as the outcome of the pregnancy is known.

If the outcome of the pregnancy is an SAE then this must be additionally reported as an SAE on the appropriate eCRF page.

Pregnancies in Female Partners of Male Subjects

Male subjects will be instructed through the ICF to immediately inform the Investigator if their partner becomes pregnant during the study and up to 3 months after the subject received the last injection of study treatment. A Pregnancy Report eCRF should be completed by the Investigator within 1 working day after learning of the pregnancy and submitted via the EDC system. Attempts should be made to collect and report details of the course and outcome of any pregnancy in the partner of a male subject exposed to the study treatment. The pregnant partner will need to sign an Authorization for Use and Disclosure of Pregnancy Health Information to allow for follow-up on her pregnancy. Once the authorization has been signed, the Investigator will update the Pregnancy Report eCRF with additional information on the course and outcome of the pregnancy. An Investigator who is contacted by the male subject or his pregnant partner may provide information on the risks of the pregnancy and the possible effects on the fetus, to support an informed decision in co-operation with the treating physician and/or obstetrician.

7.6.3 Adverse Events of Special Interest

The following safety concerns were identified as AESIs based upon either the safety data available to date for OKZ (refer to the most recent version of the Investigator's Brochure) or drug class-related events for a biologic IL-6 inhibitor:

- Infections (particularly serious infections), including TB and opportunistic infections
 - Confirmed cases of active TB must also be recorded as an SAE.

- Malignancies
 - The Investigator will be asked to provide relevant medical information/documentation (e.g., pathology/histology reports) on all malignancy cases, whether considered serious or not, as these cases will be recorded in the safety database.
- Elevation of blood lipids (e.g., hypercholesterolemia, blood cholesterol increased, blood triglycerides increased, hypertriglyceridemia, and elevation of LDL)
- Systemic injection reactions and hypersensitivity reactions, including anaphylaxis
 - Refer to Appendix 6 (Section 13.6) for details on diagnosing anaphylaxis.
- GI perforation
- CV events
- Neutropenia, thrombocytopenia, leukocytopenia, and pancytopenia
- Hepatotoxicity
 - The Investigator will be asked to provide relevant medical information/documentation (e.g., laboratory test results, including tests for viral hepatitis and, if performed, liver biopsy) on all hepatotoxicity cases, whether considered serious or not, as these cases will be recorded in the safety database (see Section 7.6.3.4).
- Injection site reactions
- Demyelination in peripheral or central nervous system
- Autoimmune disorders.

All of the events listed above will be analyzed as AESIs; some of these events are further detailed below.

7.6.3.1 Infections

Frequency, duration, and severity of infectious complications along with those requiring treatment (e.g., antibiotic, antiviral, etc) will be monitored and evaluated. Investigators will also educate subjects, parents, and/or caregivers about the symptoms of infections and will provide instructions on dealing with these infections.

Physicians should exercise caution when considering the use of OKZ in subjects with a history of recurring infection or with underlying conditions (e.g., diabetes) that may

predispose subjects to infections. Study Treatment should not be administered to subjects with active or clinically significant infection. Vigilance for timely detection of serious infection is recommended for subjects receiving biologic agents for treatment of RA, as signs and symptoms of acute inflammation may be lessened due to suppression of the acute phase reaction. Subjects must be instructed to contact their physician immediately when any symptom suggesting infection appears, in order to assure rapid evaluation and appropriate treatment. The Investigator may be asked to provide relevant medical information/documentation (e.g., result of bacterial examination or cultures).

Any infection that meets the criteria for seriousness should be reported as an SAE.

7.6.3.2 Systemic Injection Reactions, Including Anaphylaxis

A systemic injection reaction is any untoward medical hypersensitivity-like event, other than injection site reactions, occurring during or after study treatment administration that can be at least possibly attributed to the study treatment. Systemic injection reactions are further classified as acute and delayed based on timing and presentation of symptoms typical for hypersensitivity reactions.

Acute and delayed reactions to the study treatment should be reported according to the judgment of the Investigator, based on the typical clinical features.

Any systemic allergic reaction that meets the criteria for seriousness should be reported as an SAE.

Subjects will be observed for AEs at the study site during the 30 minutes following each administration of study treatment (or 2 hours after Visit 2), and subjects will be asked to contact the Investigator if any reactions occur within the 2 hours following study treatment injection.

Acute injection reactions are usually defined as at least 1 of the following signs or symptoms occurring during or within 2 hours of the study treatment injection:

- Hypotension
- Urticaria
- Flushing
- Facial or hand edema
- Throat tightness, oral cavity, or lip edema
- Headache

- Shortness of breath.

The Investigator should report any AE of acute systemic injection reaction as “anaphylaxis” if it meets the Clinical Criteria for Diagnosing Anaphylaxis, as specified in Appendix 6 (Section 13.6).

The study site must have adequate arrangements to manage anaphylactic reactions.

Delayed injection reactions are usually defined as at least 2 of the following 4 signs or symptoms occurring within 1 day to 14 days following the injection:

- Rash
- Fever (more than 100°F [38°C])
- Polyarthralgias
- Myalgias.

7.6.3.3 Gastrointestinal Perforation

Timely diagnosis and appropriate treatment may reduce the potential for complications of diverticulitis and thus reduce the risk of GI perforations. Therefore, subjects should be made aware of the symptoms potentially indicative of diverticular disease, and they should be instructed to alert their healthcare provider as soon as possible if these symptoms arise. Permanent discontinuation of study treatment is required for subjects who develop GI perforation.

Any GI perforation that meets the criteria for seriousness should be reported as an SAE.

7.6.3.4 Hepatotoxicity

The Investigator will be asked to provide relevant medical information/documentation (e.g., laboratory test results) for all serious and non-serious cases of potential hepatotoxicity.

Potential hepatotoxicity is defined as laboratory results that fulfill any of the following criteria (in all cases, AST may be substituted for ALT if ALT results are not available):

- ALT >3× to ≤5× ULN
- ALT >5× ULN
- ALT >3× ULN and total bilirubin >2× ULN

Laboratory results that satisfy any of the criteria for potential hepatotoxicity should be followed by a repeat test within 72 hours, which must include total bilirubin, direct and

indirect bilirubin, GGT, INR, alkaline phosphatase, creatine phosphokinase, and hematology assessment. After that, testing should be repeated at least weekly and followed until resolution, stabilization, or return to baseline values. Additional testing may be limited to ALT, AST, alkaline phosphatase, and bilirubin if all other laboratory results are within normal limits. The number of LFTs included in each repeat testing may be further reduced to include only those parameters which remain abnormal (i.e., abnormalities that stabilize, resolve, or return to within baseline values do not require repeat testing).

Potential hepatotoxicity events that fulfill any of the following criteria must also be recorded as SAEs in the eCRF (in all cases, AST may be substituted for ALT if ALT results are not available):

- ALT $>3 \times$ ULN and total bilirubin $>2 \times$ ULN
- ALT $>8 \times$ ULN at any time, regardless of total bilirubin or accompanying symptoms
- ALT $>5 \times$ ULN for ≥ 2 weeks, regardless of total bilirubin or accompanying symptoms
- ALT $>3 \times$ ULN, accompanied by symptoms consistent with hepatic injury (fatigue, nausea, vomiting, right upper quadrant pain or tenderness, fever, or rash)

For SAEs of potential hepatotoxicity, the Investigator should contact the Medical Monitor for guidance, as additional tests are needed to investigate all potential causes of liver toxicity (e.g., alcohol use, hepatitis infection, biliary tract disease, and concomitant medications). Work-up includes, but is not limited to:

- Obtaining a more detailed history of symptoms and prior or concurrent diseases.
- Obtaining a history of concomitant drug use (including nonprescription medications and herbal/dietary supplement preparations), alcohol use, recreational drug use, and special diets.
- Ruling out acute viral hepatitis (types A, B, C, D, and E), cytomegalovirus, Epstein-Barr virus, autoimmune or alcoholic hepatitis, nonalcoholic steatohepatitis, hypoxic/ischemic hepatopathy, and biliary tract disease.
- Obtaining a history of exposure to environmental chemical agents.
- Obtaining additional tests to evaluate liver function, as appropriate (e.g., INR, direct bilirubin, biliary tract ultrasonography/imaging results, liver biopsy).
- Considering gastroenterology or hepatology consultations.

All additional investigations should be recorded in the eCRF via the EDC system, and all records should be kept as source documents at the study site.

7.6.3.5 *Injection Site Reactions*

An injection site reaction is any untoward medical event occurring at the injection site during or after study treatment administration that can be at least possibly attributed to the study treatment (i.e., the relationship cannot be ruled out).

An assessment of pain, redness, swelling, induration, hemorrhage, and itching at the injection site will be performed by a physician and recorded on the specific page of the eCRF. At all specified visits (see Table 1 or Table 2 [as applicable]), the assessment of injection site reactions will be made prior to any administration of study treatment. All local reactions observed will be monitored until they resolve.

7.6.4 **Study Committees**

An independent DSMB and CVAC will be established for this study.

Members of the DSMB and CVAC will consist of at least 3 independent experts appointed by R-Pharm based on their expertise. Committee members will not be Investigators in the study, nor will they have any conflict of interest with R-Pharm or its designee. Members of the DSMB and CVAC will only serve on their appointed committee.

Further details (e.g., frequency of data reviews and study committee composition and membership) will be provided in the predefined DSMB Charter and a separate CVAC Charter.

7.6.4.1 *Data Safety Monitoring Board*

The independent DSMB members will perform ongoing safety surveillance and provide recommendations to R-Pharm regarding study conduct. These recommendations will be based mainly on the review of AEs and laboratory parameters. In the event that the DSMB uncovers an issue that needs to be addressed by unblinding at the treatment group level, only members of the DSMB are permitted to conduct additional analysis of the unblinded safety data.

7.6.4.2 *Cardiovascular Adjudication Committee*

The CVAC will be responsible for evaluating MACE and will remain blinded to treatment assignment. The importance of the CVAC is to ensure that all potential MACE that have been reported are judged uniformly by a single group, using the same adjudication criteria.

Data on the following fatal and nonfatal potential MACE (as further defined in the CVAC Charter) will be collected and the events will be adjudicated by the CVAC (as well as assessed by the DSMB):

- Cardiovascular death
- Non-fatal myocardial infarction
- Non-fatal stroke of all classifications
- Transient ischemic attack
- Hospitalization for unstable angina requiring unplanned revascularization
- Non-fatal coronary revascularization procedures

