6.11.1 Temporary Discontinuation of Study Treatment

The following laboratory abnormalities require prompt retesting following the reporting of the initial abnormal result (within 72 hours for abnormal LFTs and within 5 days for all other abnormal results):

- Any single ALT and/or AST elevation $>3 \times$ ULN, regardless of total bilirubin (repeat laboratory testing must include total bilirubin, direct and indirect bilirubin, gamma-glutamyl transferase [GGT], INR, alkaline phosphatase, creatine phosphokinase, and hematology assessment)
- Neutrophil count $<1000 \times 10^6/L$ ($<1000 /\text{mm}^3$)
- Lymphocyte count $<500 \times 10^6/L$ ($<500 /\text{mm}^3$)
- Platelet count $<100,000$ platelets/ mm^3
- Any single hemoglobin value <8.0 g/dL or one that drops ≥ 20 g/L (2 g/dL) below baseline

The next dose of study treatment will be held/interrupted if:

- Results from the repeat laboratory testing are not available at the time of the next scheduled dose
- ALT and/or AST remain $>3 \times$ ULN with total bilirubin $\leq 2 \times$ ULN after repeat laboratory testing and there are no symptoms consistent with hepatic injury (fatigue, nausea, vomiting, right upper quadrant pain or tenderness, fever, or rash). The Investigator may consider restarting study treatment only after discussion with the R-Pharm Medical Advisor or designee (see also Appendix 4 [Section 13.4]).

Clinically significant laboratory abnormalities should be re-tested and followed until resolution, stabilization, or return to baseline values, and the Investigator should contact the Medical Monitor for guidance regarding restarting the study treatment.

Study treatment should not be administered to subjects with active or clinically significant infections.

Temporary interruption of study treatment should also be considered if, at the discretion of the Investigator, it is necessary for safety reasons (e.g., negative trends during laboratory monitoring or remaining abnormalities after retesting which do not require premature discontinuation of the study treatment but could be harmful for the patient according to the Investigator's judgement, or other clinically significant newly diagnosed co-morbidity that

requires additional assessments for clarification of the diagnosis, and the severity of which could worsen if study treatment is continued).

The Investigator should contact the Medical Monitor for guidance regarding restarting study treatment.

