6.11.2 Permanent Discontinuation of Study Treatment

The criteria for enrollment are to be followed explicitly.

If a subject who does not meet enrollment criteria is inadvertently enrolled, R-Pharm or R-Pharm's designee must be informed immediately and the subject must immediately and permanently discontinue study treatment.

If, in the opinion of the Investigator, a subject is consistently noncompliant with the protocol in regards to study procedures, use of concomitant medications, or dosing with the study treatment, the case will be reviewed by R-Pharm on a case-by-case basis and noncompliant subjects can be discontinued from study treatment.

If the Investigator judges that the subject's health is deteriorating or not improving, the Investigator can elect to discontinue the subject from the study treatment. Appropriate standard of care, at the discretion of the Investigator, will be initiated.

In addition to the above, study treatment will be permanently discontinued in the following circumstances:

- Investigator decides that the subject should be discontinued from study treatment. If this decision is made because of an intolerable AE or a clinically significant laboratory value, the study treatment is to be discontinued, appropriate measures are to be taken, and R-Pharm or R-Pharm's designee is to be notified.
- Subject is unwilling to continue the study treatment. If the subject discontinues from the study treatment, the Investigator should inquire about the reason for discontinuing.
- Subject presents with any of the following elevated LFTs (see also Appendix 4 [Section 13.4]):
 - ALT or AST elevations $>8 \times$ ULN at any time, regardless of total bilirubin or accompanying symptoms
 - ALT or AST $>5 \times$ ULN for ≥ 2 weeks regardless of total bilirubin or accompanying symptoms
 - ALT or AST elevations $>3 \times$ ULN and total bilirubin value $>2 \times$ ULN

- ALT or AST elevations $>3 \times$ ULN accompanied by symptoms consistent with hepatic injury (fatigue, nausea, vomiting, right upper quadrant pain or tenderness, fever, or rash)
- Subject presents with any of the following laboratory abnormalities:
 - Absolute neutrophil count $<500 \times 10^6/L$ ($<500 /\text{mm}^3$)
 - Two sequential lymphocyte counts $<500 \times 10^6/L$ ($<500 /\text{mm}^3$)
 - Platelet count $<50 \times 10^9/L$ ($<50,000 /\text{mm}^3$ or $<50,000 \times 10^6/L$)
 - Two sequential hemoglobin values ≤ 8.0 g/dL and decreased ≥ 20 g/L (2 g/dL) below Screening value

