7.6.2 Serious Adverse Events

An SAE experience or reaction is any untoward medical occurrence (whether considered to be related to study treatment or not) that at any dose:

- Results in death
- Is life-threatening (the subject is at a risk of death at the time of the event; it does not refer to an event that hypothetically might have caused death if it were more severe)
- Requires subject hospitalization or prolongation of existing hospitalization
- Results in persistent or significant disability/incapacity
- Is a congenital abnormality/birth defect
- Other medically significant events, which do not meet any of the criteria above, but may jeopardize the subject and may require medical or surgical intervention to prevent 1 of the other serious outcomes listed in the definition above.
 - Examples of such events are blood dyscrasias (e.g., neutropenia or anemia requiring blood transfusion, etc) or convulsions that do not result in hospitalization.
 - Confirmed cases of active TB should be recorded and reported as SAEs.
 - Potential hepatotoxicity events that fulfill any of the following criteria should be recorded and reported as SAEs:
 - ALT >3× ULN and total bilirubin >2× ULN
 - ALT >8× ULN at any time, regardless of total bilirubin or accompanying symptoms
 - ALT >5× ULN for ≥2 weeks, regardless of total bilirubin or accompanying symptoms
 - ALT >3× ULN, accompanied by symptoms consistent with hepatic injury (fatigue, nausea, vomiting, right upper quadrant pain or tenderness, fever, or rash)

Any AE that results in an unplanned hospitalization or prolonged hospitalization should be documented and reported as an SAE. The following hospitalization scenarios are examples of events not considered to be SAEs:

- Hospitalization for a pre-existing condition, provided that all of the following criteria are met:
 - Routine treatment or monitoring of the studied indication, not associated with any deterioration in condition.
 - Elective or pre-planned treatment for a pre-existing condition that is unrelated to the indication under study and has not worsened since the start of study treatment.
 - Treatment on an emergency outpatient basis for an event not fulfilling any of the definitions of a SAE given above and not resulting in hospital admission.
 - Social reasons and respite care in the absence of any deterioration in the subject's general condition.

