7.6.6.1 Laboratory Parameters

Unless otherwise noted, the central laboratory will be used in this study to analyze routine blood samples. Blood samples will be collected according to the study Schedule of Events in Table 1 or Table 2 (as applicable).

The following laboratory parameters will be evaluated:

- CRP: Since the results of this test may unblind study staff, results from the central laboratory will be provided for Screening and baseline only. The CRP results from

samples collected during the Treatment Period will only be revealed following database lock.

- ESR: Blood for ESR will be obtained at scheduled visits and tested locally. Since the results of this test may unblind study staff, testing will be performed, reviewed, and registered by unblinded study site staff who are not responsible for managing subjects. Test results will be provided to blinded study staff for baseline only. The ESR results from samples collected during the Treatment Period will only be revealed following database lock.
- Hematology: Red blood cell count, total and differential white blood cell count, hemoglobin, hematocrit, and platelet count
- INR, aPTT, and fibrinogen
- Chemistry Panel: Urea nitrogen, creatinine, fasting glucose, calcium, sodium, potassium, bicarbonate, chloride, total protein, total bilirubin, direct bilirubin, indirect bilirubin, ALT, AST, alkaline phosphatase, GGT, and albumin
- Blood pregnancy test (at Screening for women of childbearing potential only)
- Urinary pregnancy testing (human chorionic gonadotropin) is required only for women who are of childbearing potential; may be repeated more frequently than indicated in Table 1 or Table 2 (as applicable) if required by local practices, IRB/IECs or local regulations, if a menstrual cycle is missed, or if potential pregnancy is otherwise suspected. Additional testing that is not specified in Table 1 or Table 2 (as applicable) should be reported in the eCRF as unplanned testing. Urinary pregnancy testing will be conducted locally using dipsticks provided by the central laboratory.
- Urinalysis: Specific gravity, pH, protein, glucose, ketones, blood, and leukocyte esterase
- The infectious status of the following viruses will be assessed via measurement of the parameters in parentheses (at Screening only):
 - HIV (anti-HIV1 and anti-HIV2)
 - Hepatitis B (HBsAg, anti-HBs, and anti-HBc)

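### AST alone can force permanent discontinuation, but the hepatotoxicity SAE and potential-hepatotoxicity criteria are written on ALT, so AST-led cases are not automatically captured

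*Combined protocol and SAP*

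**What the plan says.** **Rules that act on treatment.** Section 6.11.2 lists liver findings that end study treatment under the lead-in "Subject presents with any of the following elevated LFTs". There are four: above 8× ULN at any time; above 5× ULN for at least 2 weeks; above 3× ULN with total bilirubin above 2× ULN; and above 3× ULN with symptoms of hepatic injury. Each applies to either enzyme (for example "ALT or AST elevations"). The retest and hold rules in Section 6.11.1 and the table in Appendix 4 also apply to either enzyme.

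**Rules that act on reporting.** Section 7.6.2 lists the same four thresholds as SAE criteria, but on ALT, for example "ALT >8× ULN at any time, regardless of total bilirubin or accompanying symptoms". It contains no AST clause. Section 7.6.3.4 gives a laboratory definition of potential hepatotoxicity (three ALT-based criteria) and then repeats the four SAE criteria on ALT. For both it provides that "in all cases, AST may be substituted for ALT if ALT results are not available".

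**Rule that acts on investigation.** The extended search for causes in Section 7.6.3.4 is tied to the SAE label: "For SAEs of potential hepatotoxicity, the Investigator should contact the Medical Monitor for guidance".

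**Measurement.** Both enzymes belong to the same chemistry panel in Section 7.6.6.1: "indirect bilirubin, ALT, AST, alkaline phosphatase, GGT, and albumin".

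**The concern.** The same four thresholds serve two purposes, with a wider set of analytes for stopping treatment than for reporting. Because ALT and AST are on one panel, ALT should seldom be missing when AST is present, so the substitution clause will rarely apply. A subject could meet the protocol's own standard for permanent discontinuation on liver grounds and still fall outside the categories built to capture liver events uniformly.

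Hepatotoxicity is a named AESI in Section 7.6.3, and every subject takes background MTX. Section 2.2.3.2 reports AST increased among the events seen in at least 10% of subjects in some olokizumab group of RA0056. It also reports that an abnormal liver function test was the only SAE in that study's olokizumab groups judged treatment-related. At stake is whether capture, expedited reporting and cause work-up of such cases follow a fixed rule or depend on judgment at about 50 sites.

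**Working it through.** The plan states no figure on this point and no arithmetic applies. The check sets the sections side by side and traces hypothetical cases through them.

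| Section | Purpose | Analyte |
|---|---|---|
| 6.11.1 | Retest within 72 hours; hold next dose | ALT and/or AST |
| 6.11.2 | Permanent discontinuation, four criteria | ALT or AST |
| Appendix 4 | Retest, follow-up, MTX and study treatment | ALT and/or AST |
| 7.6.2 | SAE, same four thresholds | ALT |
| 7.6.3.4 | Potential hepatotoxicity; SAE, same four thresholds | ALT; AST only if ALT is unavailable |

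**Cases, with ALT measured and ≤3× ULN throughout:**

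1. AST 9× ULN.
2. AST 6× ULN for 2 weeks.
3. AST 4× ULN with total bilirubin 2.5× ULN.
4. AST 4× ULN with hepatic symptoms.

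| Rule | Cases meeting it |
|---|---|
| Permanent discontinuation (6.11.2) | 4 of 4 |
| Laboratory definition of potential hepatotoxicity (7.6.3.4) | 0 of 4 |
| Named hepatotoxicity SAE criterion (7.6.2 or 7.6.3.4) | 0 of 4 |
| 72-hour retest with extended panel (6.11.1) | 4 of 4 |
| At least weekly follow-up (Appendix 4) | 4 of 4 |

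Since no named SAE criterion is met, the Medical Monitor contact and cause work-up of 7.6.3.4 are not triggered by those criteria in any of the four cases.

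**Same AST values, with ALT missing.** Under 7.6.3.4 AST now substitutes: potential hepatotoxicity is met in 4 of 4 and an SAE criterion in 4 of 4. Under the 7.6.2 list, which has no substitution clause, a named SAE criterion is met in 0 of 4. The two SAE lists therefore give different answers for the same subject.

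**A smaller mismatch, found in passing.** For the 5× ULN criterion, 6.11.2 says at least 2 weeks and Appendix 4 says more than 2 weeks. Case 2, at exactly 2 weeks, meets the first but not the second.

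**The case against.** The strongest reply is that these cases are not lost, and much of it stands.

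- **Testing.** Section 6.11.1 requires prompt retesting for any ALT and/or AST value above 3× ULN, and "repeat laboratory testing must include total bilirubin, direct and indirect bilirubin, gamma-glutamyl transferase [GGT], INR, alkaline phosphatase, creatine phosphokinase, and hematology assessment". Section 7.6.3.4 asks for the same panel. Appendix 4 then requires at least weekly follow-up.
- **Reporting.** A clinically significant laboratory abnormality is an AE whatever the analyte (Sections 7.6.1 and 7.6.6). Section 7.6.2 allows a medically significant event to be an SAE. The reason for stopping goes into the eCRF (Section 6.11), and AEs leading to discontinuation are summarized (Section 9.4.15.1). The DSMB reviews laboratory parameters as well as AEs (Section 7.6.4.1).
- **AESI list.** Section 7.6.3 names hepatotoxicity without an ALT threshold, so an AST-led injury diagnosed by the investigator is not excluded.
- **Intent.** A stopping rule may deliberately be wider than an automatic SAE rule, since AST can rise for non-hepatic reasons.

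A reader might therefore go too far in inferring that AST-led cases are neither reported nor worked up, or that AST never counts. The documents do not support either reading.

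What remains is narrower. The AE and SAE routes above rest on investigator judgment, whereas a fixed list is meant to make reporting uniform. Retesting is not the search for causes set out in 7.6.3.4. The explicit sponsor notification in Section 6.11.2 sits in the bullet on investigator-decided discontinuation and is not attached to the liver bullet. If the narrower reporting standard is intended, the protocol does not say so, and intent would not explain why 7.6.2 and 7.6.3.4 differ.

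**Conclusion.** The inconsistency is real and can be read directly from the text. With ALT available and at or below 3× ULN, an AST-led elevation can require permanent discontinuation without being automatically captured as a hepatotoxicity SAE or as laboratory-defined potential hepatotoxicity, and without automatically triggering the Medical Monitor contact and cause work-up. Separately, the SAE lists in 7.6.2 and 7.6.3.4 disagree when ALT is missing.

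The size is unknown. The documents give no rate of AST-led elevation, so neither a number of affected subjects nor a bias in the hepatotoxicity rate can be stated. A reader might infer that the hepatotoxicity count must be biased low. That does not follow, because the AESI list has no ALT threshold and further safety-analysis details are left to the SAP (Section 9.4.15). What can be said is that complete capture of these cases is not assured by the written criteria.

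The conclusion assumes only that the criteria are applied as written. It takes no view on which enzyme or threshold is clinically right.

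**What to change.** Reconcile Sections 6.11.1, 6.11.2, 7.6.2, 7.6.3.4 and Appendix 4 so that the analytes in the SAE and potential-hepatotoxicity criteria are consistent with those that force discontinuation. Make the SAE lists in 7.6.2 and 7.6.3.4 identical, including whether and when AST may stand in for ALT. Settle the 2-week wording at the same time.

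If a narrower reporting standard is intended, state that in the protocol. Then require that every discontinuation under a Section 6.11.2 liver criterion is flagged in the eCRF and counted in the hepatotoxicity AESI summary, with the counting rule written into the SAP.

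The cost is a few words in the affected sections and an edit check in the data capture system. Aligning the reporting criteria could bring in a few additional reports for AST rises of non-hepatic origin. It could also widen the set of subjects who enter the Medical Monitor contact and cause work-up, so the choice of rule is a clinical decision for the sponsor.
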